6.2. Lesion injection

- All personnel handling talimogene laherparepvec or material contaminated with talimogene laherparepvec must observe safety precautions (e.g., wear a laboratory coat, safety glasses and gloves) in accordance with local/regional or BSL classification guidelines for administration.
- Inject talimogene laherparepvec intralesionally (Table 4.):
 - a) A single point of insertion is recommended; multiple insertion points may be used if the tumor is larger than the radial reach of the needle.
 - b) Talimogene laherparepvec should be injected along multiple different tracks within the lesion in order to obtain as wide a dispersion as possible.
 - c) Distribute talimogene laherparepvec within the lesion through the insertion point using the radial reach of the needle in different directions to evenly distribute.
- Avoid premature extraction of the needle.
- After dosing, the injection site should be swabbed with alcohol and pressure should be applied with gauze for several seconds after injection.
- The injection site should be covered with an absorbent pad and dry occlusive dressing. Please ensure a fresh pair of gloves is worn when handling the absorbent pad and dressing to prevent cross contamination with talimogene laherparepvec. Please also ensure that the outside of the dressing is wiped down with an alcohol swab to further minimize any cross contamination.
- Discard materials used during injection (eg, gloves, needles, gauze) in accordance with local/regional or BSL classification guidelines.

Table 4. Schematic illustration of Talimogene laherparepvec injection

6.3. Dose management

Subjects should be assessed clinically for adverse events/toxicity prior to each dose using the Common Terminology Criteria for Adverse Events (CTCAE) version 4.0. Complete blood count with differential and chemistry panels including liver function laboratory tests (ALT, AST, and total bilirubin) should be obtained according to the schedule of assessment in the protocol, and

the results should be checked before each scheduled dose of talimogene laherparepvec. Dosing will occur only if these test values are acceptable per the protocol.

6.3.1 Dose Limiting Toxicities (DLTs)

Toxicity should be evaluated according to CTCAE version 4.0. DLTs should be defined based on CTCAE and should include events assessed as related to talimogene laherparepvec during treatment and up to 4 weeks after the last talimogene laherparepvec injection.

The following herpetic events are defined as DLTs:

- Serious herpetic events such as herpetic encephalitis, encephalomyelitis or disseminated herpetic infection.
- Any herpetic event confirmed related to talimogene laherparepvec that requires treatment with acyclovir or similar anti-viral agent, Talimogene laherparepvec treatment should be suspended if treatment is required with systemic acyclovir or other anti-virals, If ongoing treatment is required, talimogene laherparepvec treatment should be permanently discontinued. Herpetic events due to wild-type HSV-1 or wild-type HSV-2 which require acyclovir and are not due to talimogene laherparepvec (as confirmed by PCR testing) should not be considered as DLTs caused by talimogene laherparepvec
- Grade 3 or greater immune-mediated adverse events
- Any grade plasmacytoma at or near the injection site or evidence of impaired wound healing at the injection site
- Grade 3 or greater allergic reactions considered at least possibly related to talimogene laherparepvec
- Grade 4 non-hematologic toxicity.
- Grade 3 non-hematologic toxicity lasting > 3 days despite optimal supportive care;
 - Grade 3 fatigue will not be classified as DLT, irrespective of duration.
- Any Grade 3 or higher non-hematologic laboratory value if the abnormality:
 - fails to respond to medical intervention, or
 - leads to hospitalization, or
 - persists for > 1 week unless deemed not clinically important per both investigator and sponsor.
- Grade 3 or 4 febrile neutropenia.
- Grade 4 thrombocytopenia associated with a bleeding event deemed at least possibly related to talimogene laherparepvec and requiring intervention.
- Any other intolerable toxicity leading to permanent discontinuation of talimogene laherparepvec.
- Grade 5 toxicity (i.e. death).

If an unexpected DLT deemed at least possibly related to talimogene laherparepvec occurs, talimogene laherparepvec administration should be delayed until the DLT has resolved to at least CTCAE (v. 4.0) grade 1 or has returned to baseline.

All necessary supportive care shall be available to subjects. Additional treatment modifications should be considered depending upon the subject's clinical situation. Talimogene laherparepvec treatment should be continued based on the potential risk/benefit assessment of the subject.

6.3.2. Dose reduction

Dose reductions with regards to changes in the concentrations of talimogene laherparepvec are not permitted. However, patients may require a reduction in the volume injected due to a disease response or due to local toxicity at the injection site. However, if in the course of administration of talimogene laherparepvec the subject cannot tolerate the full dose due to an injection-related adverse event such as pain, the total volume given should be recorded, and the reason for intolerance should be documented as an adverse event.

6.3.3 Dosage Adjustments, Delays, Rules for Withholding or Restarting
If talimogene laherparepvec treatment was delayed by >2 week, that dose will be deemed to have been missed and the subject will proceed to the next scheduled treatment visit.

Dose reductions of talimogene laherparepvec is not permitted, other than a reduction in the volume injected due to a disease response.

If a subject experiences any of the following treatment-related toxicities, talimogene laherparepvec administration should be delayed until the toxicity has resolved to at least CTCAE grade 1 or baseline:

- Grade 2 or greater immune-mediated adverse events, with the exception of vitiligo.
- Grade 2 or greater allergic reactions.
- Any other grade 3 or greater hematologic or non-hematologic toxicity.

Subjects who are receiving talimogene laherparepvec may not receive systemic antiherpetic drugs (eg, acyclovir, valacyclovir, famciclovir), but may receive a topically administered antiherpetic drug more than 20 cm from a talimogene laherparepvec injection site. Dosing should be permanently discontinued if, in the opinion of the investigator, the subject develops clinical evidence of any systemic herpes infection (such as encephalitis or disseminated infection).

If the subject requires corticosteroid dosing of >10 mg prednisone daily (or equivalent, eg, 1.5 mg dexamethasone) for any reason, talimogene laherparepvec dosing must be withheld until the corticosteroid dose has decreased to <10 mg prednisone daily (or equivalent).

Talimogene laherparepvec treatment should be continued based on the potential benefit/risk assessment of the subject.

If talimogene laherparepvec dosing is delayed by more than 6 weeks from the date of the planned dose (i.e., approximately 8 weeks from the previous dose) due to the occurrence of an adverse event that is considered related to talimogene laherparepvec, the subject must be permanently withdrawn from talimogene laherparepvec treatment.

If talimogene laherparepvec dosing is delayed by more than 6 weeks from the date of the planned dose (i.e., approximately 8 weeks from the previous dose) for reasons other than treatment-related toxicity, the case must be reviewed by the principle investigator to determine if the subject can resume talimogene laherparepvec therapy.

Patient will be allowed to continue, capecitabine, hormonal therapy and/or anti-HER-2 therapy while receiving study drug.

6.4 Permanent Discontinuation of Treatment and Withdrawal of patients from study

Talimogene laherparepvec is to be permanently discontinued for patients meeting any of the following criteria:

- The patient, for any reason, requires treatment with another anticancer therapeutic agent for the study disease (other than the exceptions noted in the protocol, if applicable). In this case, discontinuation from the treatment occurs immediately upon the introduction of the new agent.
- Confirmed PDA grade 2 or greater Immune-mediated adverse events (with the exception of vitiligo) or allergic reactions attributed to talimogene laherparepvec that would require a dose delay of greater than 6 weeks from the date of the planned dose (i.e., approximately 8 weeks from the previous dose).
 - Note: immune-mediated glomerulonephritis, vasculitis, and pneumonitis and exacerbation of psoriasis have been observed in subjects receiving talimogene laherparepvec in clinical trials. Most of these subjects had a history of other autoimmune disease and/or prior treatment with agents that offered plausible alternative etiologies, however, immune-mediated adverse events can potentially involve any organ system.
- Any other talimogene laherparepvec-related non-hematologic or hematologic toxicities grade 3 or greater occur that, in the opinion of the investigator, would require a dose delay of greater than 4 weeks from the date of the planned dose (i.e., approximately 6 weeks from the previous dose).
- The subject develops clinical evidence of any systemic herpes infection (such as encephalitis or disseminated infection).
- A female subject becomes pregnant or fails to use acceptable method(s) of effective contraception (for those subjects who are able to conceive).
- A female subject breast feeds while on study treatment.
- Concurrent medical illness that, in the judgment of the investigator, would make continued treatment with talimogene laherparepvec dangerous for the subject.
- For additional information related special warnings and precautions for the use of talimogene laherparepvec please refer to the latest version of the Talimogene Laherparepvec Investigator's Brochure.
- Dosing noncompliance: If dosing compliance is not 100% (administration of talimogene laherparepvec on the scheduled date +/- 3 days in the absence of toxicity), the study treatment should be discontinued for the patient.
- Complete remission of locally recurrent disease with or without distant disease
- Patient withdraws consent. In the event that a patient withdraws consent, the reason(s) for withdrawal must be documented. Patients must be informed that their participation in the

study is voluntary and that they may choose not to take part in the study or to stop taking part at any time. If a patient chooses not to take part in the study or to stop at any time, his/her future medical care or medical benefits will not be affected.

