8.0. Evaluation during study

The window for all assessments and treatments should be completed within 5 days of the scheduled time.

Patients will be allowed to continue current hormonal therapy, selected chemotherapy, targeted agents and/or anti-HER-2 therapy, which will be administered as standard of care, (per physician discretion) while receiving study drug.

8.1. Evaluation during talimogene laherparepvec:

- 8.1.1. Patients will have a CBC, differential count and platelet count before each cycle.
- 8.1.2. Patients may repeat the CBC, differential count and platelet count until recovery of these measures before the next cycle (absolute neutrophil counts \geq 1,000 and platelets \geq 100,000 per mm³).
- 8.1.3. Medical history and physical examination with vital signs, weight, and PS before cycles 2 and 5 and every additional 2 cycles of treatments.
- 8.1.4. Digital photography of chest lesions before cycles 2, 5, and every additional 2 cycles of treatment.
- 8.1.5. Toxic effects will be assessed before each cycle.
- 8.1.6. SMA (Na, K, BUN, creatinine, Mg, calcium, AST, ALT, glucose, LDH, and total bilirubin) will be performed before each cycle.
- 8.1.7. Levels of tumor markers (e.g., cancer antigen CA 27.29) will be assessed before cycle 5 and every additional 4 cycles of treatment.
- 8.1.8. Systemic immunity in serum or plasma levels of GM-CSF, IL-2, IL-12, TNF-alpha (α), IFN- alpha (α); and phenotype for T-cell subsets (CD3, CD4, CD8, CD25), and NK-cell subsets (CD16, CD56) will be determined via multiparameter FACS analysis (percentage and absolute numbers) before cycle 5 and at the end of study in [name] laboratory at MD Anderson.
- 8.1.9. PET-CT or CT of bone/ abdomen/chest should be performed before cycle 5 and before every additional 4 cycles of treatment as clinically indicated.
- 8.1.10. Disease assessment will be done at the end of cycle 4, cycle 8 and cycle 10.

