8.3 Study Calendar

Evaluation and treatment	Screening	Cycle 1 Day 1	Cycle 2 (D22+/-5 days)	Cycle 5 (D64 +/- 5 days)	Cycle 7 and every 2 cycles	Follow up⁹
Time	Baseline (within 6 weeks)	Prior to talimogene laherparepvec injection				
Eligibility, screening, consent, and registration	X					Patients will be monitored for 1 year after removal from the study or until death, whichever occurs first.
Medical history	X					
Staging with tumor measurements	X					
Photography of chest wall	X ¹		X	X	X	
Biopsy of local recurrence [HE, IHC]	X ⁸			X ⁸		
Biopsy of easily accessible distant metastasis [HE, IHC]				X ⁸		
Correlative immune study	X			X ⁷		
Physical examinations, vital signs	X	X ²	X	X	X	
ECOG PS	X	X ²	X	X	X	
Hematology assessment and Biochemical profiles ^{3,5}	X	X ²	X	X	X	
Tumor markers (CA27.29) ¹¹ , IgG (baseline only)	X			X	X ¹¹	
Chest X-ray; Breast sonography ¹³	X					
Pregnancy test if applicable ¹⁰	X					
PET-CT or CT scan of bone/abdomen/chest as clinically indicated	X			X	X ⁴	
Disease assessment ¹²				X	X	

Adverse events ⁵	X	X	X	X	X	
Talimogene Laherparepvec injection ⁶		X	X	X	X	

1. Within 1 week prior to treatment
2. No need to repeat if within 7 days from baseline
3. Hematology include CBC, differential count and platelet count; and biochemical profiles SMA include Na, K, BUN, creatinine, Mg, calcium, AST, ALT, LDH, total bilirubin
4. Repeat every 4 cycles as clinical indicated
5. Before each cycle. Reporting exposure to talimogene laherparepvec and should be collected for the duration of the study and safety f/u
6. Starting cycle 2, Talimogene Laherparepvec injection will be given every 2 weeks until disease progression
7. Correlative immune study will be repeated before cycle 5 and at the end of study if available.
8. Core biopsy of local recurrence at baseline if samples (i.e., paraffin block or 5-10 unstained slides) from the local recurrence are not available. Core biopsy of either distant metastasis or local recurrent lesions before cycle 5 based on patient status.
9. a. Safety Follow-Up: should be conducted approximately 30 days after the last dose of trial treatment or before the initiation of a new anti-cancer treatment, whichever comes first. Safety Follow-Up Visit can be done in the clinic, or by phone if patient is not willing to come to the clinic for follow up.
- b. Unexpected AEs: Patients removed from study for unexpected adverse events will be monitored until AE is resolved or stabilized.

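### A non-toxicity dose 4 or 5 days off schedule is inside the treatment window of section 8.0 but is a ground for permanent discontinuation in section 6.4, and the longer delays that section 6.3.3 tolerates conflict with 6.4 as well

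*Combined protocol and SAP*

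**What the plan says.** **Section 6.4.** The list opens with "Talimogene laherparepvec is to be permanently discontinued for patients meeting any of the following criteria". One bullet is dosing noncompliance: if compliance falls below 100%, the study treatment should be discontinued. Compliance means "administration of talimogene laherparepvec on the scheduled date +/- 3 days in the absence of toxicity".

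**Section 8.0.** "The window for all assessments and treatments should be completed within 5 days of the scheduled time". Treatments are named, so this is not a window for assessments only.

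**Section 8.3, study calendar.** Two column heads carry a window, "Cycle 2 (D22+/-5 days" and "Cycle 5 (D64 +/- 5 days" (closing bracket omitted). Both columns have a mark in the injection row. Footnote 6 sets the spacing: "Starting cycle 2, Talimogene Laherparepvec injection will be given every 2 weeks until disease progression". No window is printed for the other dosing columns.

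**Section 6.3.3.** "If talimogene laherparepvec treatment was delayed by >2 week, that dose will be deemed to have been missed and the subject will proceed"; in other words, treatment picks up again at the following visit. If the delay exceeds 6 weeks "for reasons other than treatment-related toxicity, the case must be reviewed by the principle investigator to determine if the subject can resume". The section also has a general sentence that ties continuation of treatment to a benefit/risk assessment.

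**Section 6.5.1.** Injections are to continue for at least 10 cycles (about 5 months) unless disease progression is uncontrolled. The reason given is a median time to response of 4.1 months in an earlier single-agent study, with half of the responders progressing first.

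No section says which window or rule prevails.

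**The concern.** Sections 6.4 and 8.0 govern the date of the same injection and give different answers for a slip of 4 or 5 days. One calls the dose on time; the other makes it a reason to end treatment. Two investigators could handle identical patients differently and both be following the protocol.

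For delays that are purely logistic, 6.3.3 and 6.4 collide too. The missed-dose rule and the investigator review have nothing to act on if a dose 4 days late has already ended treatment.

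At stake are late responses. A patient taken off treatment for scheduling reasons does not receive the 10 cycles that 6.5.1 regards as needed to see a response. Responses already reached are not affected. The design rejects the treatment at 3 or fewer responders in 35, so single responses count.

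**Working it through.** **1. The windows side by side**

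| Scheduled day | 8.0 and calendar (+/-5) | 6.4 (+/-3) | Days permitted by one, noncompliant in the other |
|---|---|---|---|
| Cycle 2, day 22 | 17 to 27 | 19 to 25 | 17, 18, 26, 27 |
| Cycle 5, day 64 | 59 to 69 | 61 to 67 | 59, 60, 68, 69 |

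The same 4- and 5-day slips conflict at every other cycle after the first, on the strength of 8.0 alone.

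**2. Longer logistic delays**

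| Delay, no toxicity | 6.3.3 | 6.4 |
|---|---|---|
| More than 2 weeks | dose counted as missed, patient goes on | ground for permanent discontinuation |
| More than 6 weeks | investigator review, may resume | ground for permanent discontinuation |

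If the delay is due to an adverse event unrelated to the drug, 6.4's restriction to the absence of toxicity may exempt it. The clear conflict is therefore for purely logistic causes.

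**3. Where a late response falls in the schedule**

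With doses on day 1, day 22 and every 14 days after that, dose 9 is on day 120 and dose 10 on day 134. The cited median is 4.1 x 30.44 = day 125, between the two. Section 9.4 attributes these figures to a phase III melanoma study, so their relevance to breast cancer is assumed.

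**4. The plan's own design figures (section 13.1)**

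Stop if 0 of 13 respond; reject if 3 or fewer of 35 respond. The probability of a positive result is the sum over x = 1 to 13 of P(X1 = x) x P(X2 >= 4 - x), with X1 binomial(13, p) and X2 binomial(22, p).

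- At p = 5%: 8.4%; early stop 0.95^13 = 51.3%; expected sample size 23.7.
- At p = 20%: 90.3%; early stop 0.80^13 = 5.5%; expected sample size 33.8.

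These agree with the plan. None of them depends on the dosing window.

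**5. Illustration only**

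The documents give no rate of off-window doses and no fraction of responses lost after stopping. Assume that:

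- a share q of doses breaches +/-3 days without toxicity, independently of each other and of response;
- every breaching patient is removed;
- patients otherwise stay on treatment to cycle 10;
- a fraction f of the responses is lost among patients who breach at any of doses 2 to 9.

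Patients breaching at least once in doses 2 to 10: 1 - (1 - q)^9. Response rate: 0.20 x (1 - f x [1 - (1 - q)^8]). Power is then recomputed as in step 4.

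| q | Patients breaching by cycle 10 | Power, f = 10% | f = 25% | f = 50% |
|---|---|---|---|---|
| 1% | 8.6% (3.0 of 35) | 90.0% | 89.5% | 88.6% |
| 2% | 16.6% (5.8 of 35) | 89.7% | 88.7% | 86.8% |
| 5% | 37.0% (12.9 of 35) | 88.8% | 86.3% | 80.9% |

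Against 90.3%, the loss runs from 0.3 to 9.4 points, depending on two numbers that the documents do not supply. Aligning the window helps only the 4- and 5-day slips among these breaches; the remainder depends on the 6.3.3 clarification.

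**The case against.** **Enforcement.** The 6.4 bullet says 'should', and 6.3.3 ties continuation to a benefit/risk assessment, so automatic removal is not certain. This stands, and it limits any claim about consequences. It does not remove the conflict, because the opening line of the list is mandatory and nothing ranks the two sections.

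**A tempting stronger reading: a measurable loss of power.** A reader might infer that the trial gives up as much as 9.4 points. The documents do not support that. The figure needs 5% of doses off-window, every breaching patient removed, and half of those patients' responses lost. Section 6.5.2 notes that responses to immunotherapy can come late, so stopping injections need not erase a later response.

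**Direction.** A reader might also infer that the effect can only work against the drug. For the count against 3 of 35 that is right: lost responses lower the count and do not raise the 8.4% type I error. The estimated response rate is less clear. Section 13.1 reports it in evaluable patients, and section 9.7.3 makes substantial schedule deviators non-evaluable without calling them failures. If discontinued patients were classed there, the estimate could move either way.

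**The tighter window may be deliberate.** If windows are anchored to scheduled dates, +/-5 days around 14-day dosing allows injections on day 27 and day 31 (36 - 5), only 4 days apart. With +/-3 days the closest pair is day 25 and day 33, 8 days apart. Section 4.1 reports that 2- to 3-week spacing was chosen with side effects and viral replication in mind. This stands as a reason not to widen 6.4 without a safeguard.

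**Steroid holds.** One might count a hold that 6.3.3 requires as noncompliance under 6.4. Following a mandated hold is arguably not noncompliance, so the point does not rest on it.

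**Conclusion.** The conflict is on the face of the text. A non-toxicity dose 4 or 5 days off schedule is permitted by 8.0 (and by the calendar at cycles 2 and 5) and is a ground for permanent discontinuation in 6.4. For purely logistic delays, 6.3.3 and 6.4 also disagree.

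The consequence is conditional: if 6.4 is applied literally, patients can leave before 10 cycles and late responses can be lost. How many cannot be estimated from the documents, and the power figures above illustrate the mechanism only. Confidence is high for the inconsistency and low for its effect. Severity is low to moderate: an affected patient loses treatment permanently, but the rule may seldom be enforced.

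**What to change.** - **One window.** Use the same dosing window in 6.4, 8.0 and the calendar. By default, change 6.4 to +/-5 days, which already stands in the other two places.
- **Minimum interval.** With +/-5 days, state a minimum interval between consecutive injections, so that they cannot fall 4 days apart. The sponsor should set it on clinical grounds.
- **Delays under 6.3.3.** State in 6.4 that delays handled under 6.3.3 are not dosing noncompliance and do not by themselves require permanent discontinuation.
- **Alternative.** If the sponsor wants +/-3 days for injections, correct 8.0 and the calendar instead, and treat a breach as a recorded deviation, not a ground to stop.

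The cost is protocol wording: one number, one sentence on 6.3.3 and one on the minimum interval, which needs a short clinical decision. Sample size, endpoint and analysis do not change.

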Within the guidelines of the algorithm in Table 3 and the prioritization model above, each lesion should be injected with the maximum amount possible at each visit before moving on to the next lesion, subject to tumor-specific limitations (such as the inability to inject the full amount into the lesion). Lesions should be injected until the maximum volume per day (4.0 mL) has been reached or there are no further injectable lesions, whichever comes first.

Lesion site preparation

- Talimogene laherparepvec is to be administered only by intralesional injection into cutaneous, subcutaneous and nodal lesions with or without image ultrasound guidance. Talimogene laherparepvec must not be administered into visceral organ metastases.
- The injection site may be pre-treated with a topical anesthetic agent or an injectable local anesthetic; however, a local anesthetic must not be injected directly into the lesion. Please note that the anesthetic should not be mixed together with talimogene laherparepvec in the same syringe. Talimogene laherparepvec does not require any routine premedication.
- Swab the lesion and surrounding areas with alcohol, allow to dry.
- Talimogene laherparepvec is administered by HCP

Figure 4: Timeline of talimogene laherparepvec injection

* Talimogene laherparepvec is administered lower dose for the first course due to possible sero-negative status.

** Biopsy from local disease.

*** Biopsy from distant metastases if available or local disease of non-injection site (optional)

[figure not shown]
Table 3. Talimogene laherparepvec injection volume guideline based on tumor size

Tumor Size (longest dimension)	Maximum Injection Volume
> 5.0 cm	4.0 mL
> 2.5 cm to 5.0 cm	2.0 mL
> 1.5 cm to 2.5 cm	1.0 mL
> 0.5 cm to 1.5 cm	0.5 mL
\leq 0.5 cm	0.1 mL

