6.5 The end of study

6.5.1. Definition of the end of the study

Previous talimogene laherparepvec single agent study showed that the median time to response was 4.1 months, and 50 % of these responders had progressive disease (PD) (defined by modified WHO criteria) prior to response. In this study talimogene laherparepvec administration will continue for at least 10 cycles (approximately 5 months) unless uncontrolled disease progression is observed. Beyond 10 cycles, progressive disease will be measured based on RECIST ver1.1.

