9.0. Criteria for response, overall response and disease control

Response must be evaluated using RECIST ver.1.1. Tumor lesions must be accurately measured in at least one dimension (longest diameter in the plane of measurement is to be recorded) with a minimum size of 10 mm by CT scan (irrespective of scanner type) and magnetic resonance imaging (MRI) (*no less than double the slice thickness and a minimum of 10 mm*), 10 mm caliper measurement by clinical examination (when superficial), and 20 mm by chest X-ray (if clearly defined and surrounded by aerated lung).

Tumor lesions must be accurately measured in at least one dimension of local recurrence and skin metastases if applicable. These will be measured by caliper, and the extent of disease should be recorded on a photograph with a scale marker and injection marker. If these lesions are immeasurable, their extent should also be recorded on a photograph with a scale marker and injection marker to assess the rate of overall response.

9.1. Complete Response (CR): Disappearance of all target and non-target lesions at a minimum of 4 weeks.

9.2. Partial Response (PR): At least a 30% decrease in the sum of the longest diameter of the target lesions at a minimum of 4 weeks, taking as a reference the baseline sum of the longest diameter with target.

9.3. Stable Disease (SD): Neither sufficient shrinkage to qualify for PR nor sufficient increase to qualify for progressive disease (PD), taking as a reference the smallest sum of the longest diameter since the treatment started with target lesions.

9.4. Progressive disease (PD): At least a 20% increase in the sum of diameters of target lesions, taking as reference the smallest sum on study (this includes the baseline sum if that is the smallest on study). In addition to the relative increase of 20%, the sum must also demonstrate an absolute increase of at least 5 mm. (Note: the appearance of one or more new lesions is also considered progression). In the previous phase III melanoma study, PD (defined by modified WHO criteria) prior to response was observed in about 50% of responders, and median time to response was 4.1 months. Thus, for this study purpose, a true PD will be confirmed at the end of cycle 10 (approximately 5 months) as long as patients tolerated the treatment.

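### Sections 6.4, 6.5.1 and the study calendar disagree on treatment after local complete remission, and a patient stopped early for remission has no clearly scheduled assessment to confirm response

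*Combined protocol and SAP*

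**What the plan says.** **Treatment duration**

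- Section 6.4 lists, among the grounds for permanent discontinuation, "Complete remission of locally recurrent disease with or without distant disease". Its title covers both stopping treatment and withdrawal from the study.
- Section 6.5.1 says that "talimogene laherparepvec administration will continue for at least 10 cycles (approximately 5 months) unless uncontrolled disease progression is observed". Its stated background is an earlier study in which median time to response was 4.1 months and half of the responders had progressed before responding.
- Footnote 6 of the calendar in 8.3 says that, from cycle 2, "Talimogene Laherparepvec injection will be given every 2 weeks until disease progression".
- Section 6.1 limits where the drug can go: "Talimogene laherparepvec must not be administered into visceral organ metastases". On each treatment day, injection goes on until the volume limit is reached or no injectable lesion is left.

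**Response**

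- CR (9.1) is "Disappearance of all target and non-target lesions at a minimum of 4 weeks". PR (9.2) is "At least a 30% decrease in the sum of the longest diameter of the target lesions at a minimum of 4 weeks".
- Local disease contributes to the score. Section 9.0 says "Tumor lesions must be accurately measured in at least one dimension of local recurrence and skin metastases if applicable".
- The primary endpoint (9.5, 13.1) covers all disease. Non-measurable sites must reach CR, and measurable sites CR or PR. PD is confirmed at the end of cycle 10 (9.4, 9.5).

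**Assessment schedule**

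- Section 8.1.10 and calendar footnote 12 set disease assessment at the ends of cycles 4, 8 and 10. Section 8.1 is headed as evaluation during treatment. Section 13.1 equates the three times with 2, 4 and 5 months.
- Calendar footnote 9 describes follow-up after treatment: a safety contact at about 30 days, follow-up of unexpected adverse events, and survival by chart or phone for up to 1 year. Section 9.11 says patients are monitored for 1 year and does not mention tumour assessment.

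**The concern.** Take a patient whose local disease has disappeared at the end of cycle 4. Section 6.4 stops the drug. Section 6.5.1 and footnote 6, read on their own, continue it. Two sites, or two investigators at one site, could treat this patient differently and each cite the protocol.

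The statistical stake is the primary endpoint. A CR or PR first seen at that visit still has to be shown to last 4 weeks. The next visit that could show this is the end of cycle 8, and a patient off treatment has no cycle 8. The same holds for the month-5 evaluation, when remaining distant disease would be scored and an apparent PD confirmed or overturned. If the visits do not happen, the lost information comes from patients with a strong local effect, and the observed response rate can only move down. The decision rule turns on small counts (zero of 13, then 3 or fewer of 35), so one unrecorded response could change the outcome.

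**Working it through.** **1. Planned assessment times on the calendar.** Cycle 2 is day 22 and later cycles follow every 14 days (6.1, 8.3), so cycle *k* starts on day 22 + 14(*k* − 2). The end of a cycle is taken as the start of the next.

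- End of cycle 4: 22 + 14 × 3 = day 64
- End of cycle 8: 22 + 14 × 7 = day 120
- End of cycle 10: 22 + 14 × 9 = day 148

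The gaps are 56 days (8 weeks) and 28 days (4 weeks). These times match the 2, 4 and 5 months in 13.1.

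**2. Who is exposed?** Set the stop in 6.4 against the response definitions.

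- *No distant disease.* Complete local remission is overall CR once it has lasted 4 weeks. Only the confirming visit is at risk.
- *Measurable distant disease.* Suppose all lesions are targets and distant disease is unchanged. The target sum then falls by local / (local + distant). Illustrative baselines: 30/(30 + 50) = 37.5%, PR; 30/(30 + 70) = 30%, PR just met; 30/(30 + 100) = 23%, not PR. So PR is reached through local disease alone when that is at least 30% of the baseline sum. It still has to last 4 weeks.
- *Bulky or non-measurable distant disease.* Local remission is not enough. Overall response needs a later distant response (CR at non-measurable sites), which nobody is clearly scheduled to measure once injections end.
- *PR at day 64, local CR at day 120, PR maintained.* Eight weeks are already documented, so the response is confirmed.
- *Local CR first seen at day 148.* This is the last scheduled assessment, so the 6.4 stop removes nothing.

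The exposed patients are those with an early local CR not yet confirmed, and those with bulky or non-measurable distant disease.

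**3. The plan's own operating characteristics.** Inputs from 13.1: 13 patients in stage 1, stop at 0 responses; 22 more; reject at 3 or fewer of 35; rates 5% and 20%.

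- P(early stop) = (1 − p)^13
- P(promising) = Σ over x ≥ 1 of P(X₁ = x) × P(X₂ ≥ 4 − x), with X₁ ~ Bin(13, p) and X₂ ~ Bin(22, p)
- Expected N = 13 + 22 × (1 − P(early stop))

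| True rate | Early stop: plan / recomputed | Promising: plan / recomputed | Expected N: plan / recomputed |
|---|---|---|---|
| 5% | 51% / 51.3% | 8.4% / 8.4% | 23.7 / 23.7 |
| 20% | 5% / 5.5% | 90% / 90.3% | 33.8 / 33.8 |

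The stated design figures reproduce.

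**4. Sensitivity only.** Let *f* be the share of true responders whose response is never confirmed. The documents do not give *f*; the values below are assumptions. The observable rate is 0.20 × (1 − *f*), put through the same rule.

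| Assumed *f* | Observable rate | Power | Stage 1 stop |
|---|---|---|---|
| 0 | 20% | 90.3% | 5.5% |
| 2.5% | 19.5% | 89.2% | 6.0% |
| 5% | 19% | 88.0% | 6.5% |
| 10% | 18% | 85.4% | 7.6% |
| 20% | 16% | 78.4% | 10.4% |
| 25% | 15% | 74.0% | 12.1% |

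**The case against.** **Section 6.5.1 may be a default, with 6.4 as its exceptions.** Read as exhaustive, 6.5.1 would also contradict the stops in 6.4 for pregnancy, systemic herpes infection, toxicity and withdrawn consent, which cannot be intended. And when local disease has gone there may be nothing left to inject, so 6.5.1 could not be carried out. This is fair, and it softens the conflict. It does not remove it. No passage says that remission is an exception to the 10-cycle minimum, footnote 6 gives a third rule, and a patient may still have injectable skin or nodal lesions elsewhere.

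**The bullet in 6.4 may mean remission of all disease, local and any distant.** The wording allows this. The patient is then a CR once 4 weeks have passed. The difference in duration and the need for a confirming visit both remain.

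**A reader might infer that these patients cannot be scored as responders.** The documents do not support that. Section 9.7 does not list a stop for remission among the non-evaluable categories, the operative sentence of 6.4 stops the drug and not the assessments, 13.1 gives evaluation times in months, and an investigator may still measure the patient. What stands is narrower: no provision clearly schedules that measurement.

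**A reader might also infer that the trial is underpowered.** It is not shown to be. The 90% is correct, and any loss depends on a share that no document gives. At the low end of the range the loss is about 1 to 2 percentage points.

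**Conclusion.** The point holds in two limited parts. First, 6.4, 6.5.1 and calendar footnote 6 give different accounts of treatment after local complete remission and must be reconciled. The documents do not settle which is meant, and that is a clinical decision for the sponsor. Second, a patient whose injections end early for remission has no clearly scheduled assessment to confirm a 4-week CR or PR, or to score remaining distant disease and confirm PD at month 5. This rests on the cycle-based schedule and on a follow-up section that is silent about tumour assessment. It is a gap in the text, not a bar to scoring.

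The size is unknown. The loss can only lower the observed rate, and it is confined to the exposed groups identified above. If 2.5% to 25% of true responders went unconfirmed, power at a true 20% rate would lie between 89.2% and 74.0%, and the chance of stopping at stage 1 between 6.0% and 12.1%, against 90.3% and 5.5% with no loss. The upper end would need a quarter of all responders both to stop for remission and to go unmeasured, which nothing in the documents indicates. Severity is moderate: the endpoint definition, decision rule and sample size stand, but the primary endpoint deserves a clear measurement rule for these patients.

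**What to change.** - Reconcile 6.4, 6.5.1 and calendar footnote 6 on what happens at local complete remission, with and without distant disease. Say whether the 6.4 bullet means local disease or all disease, and state in 6.5.1 which 6.4 stops override the 10-cycle minimum. The choice of rule is the sponsor's.
- Whichever rule is kept, separate stopping the drug from leaving the study. State in 8.1.10, the calendar and 9.1–9.2 that patients whose injections end for remission stay on study for response. They keep disease assessments at the planned calendar times (about days 64, 120 and 148), covering local and distant disease, with one at least 4 weeks after first CR or PR.

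The cost is wording in a few places and one or two ordinary tumour measurements in the few patients concerned. The sample size and the two-stage rule do not change.
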